**1.4 Rationale**

Chemotherapy resistance is a major cause of death in patients with relapsed or refractory AML. CPI-613 can increase the sensitivity of leukemia cells to chemotherapy in petri dishes and mice. As a single agent in a phase I clinical trial several relapsed/refractory AML patients had an objective response. Additionally, a phase I study of CPI-613 in combination with high dose cytarabine and mitoxantrone has recently been completed. This trial established the MTD of CPI-613 as 2,500 mg/m^2. Preliminary analysis of the study revealed an overall complete remission or complete remission with incomplete count recovery rate of 45%. This compares favorably with our historical experience of this regimen without CPI-613. In this trial patients with poor risk cytogenetics had a 46% response rate, far superior to the 19% response seen with historical data. This trial established that CPI-613 can be safely administered at 2,500 mg/m^2 in this combination and results in superior response rates. The novel mechanism of action, non-cross resistance with chemotherapeutic agents, lack of CPI-613-related myelosuppression clinically and increase response rate make this regimen a suitable candidate for the proposed pilot study.

### **1.5 Justification of the Dose of CPI-613**

WFUCCC 22112, a phase I study of CPI-613 in combination with high dose cytarabine and mitoxantrone given exactly as proposed in the current study established the MTD of CPI-613 to be 2,500 mg/m^2. A detailed analysis of the response data indicated that similar response rates were seen at the 2,000 mg/m^2 dose with less toxicity. Further studies have indicated a dose of 1500 mg/m^2 has a similar efficacy profile as 2,000 mg/m^2 but with even less toxicity. The rationale behind using a dose of 500mg/m^2 is supported by three lines of evidence: 1) pre-clinical evidence in mice suggesting lower doses may be more efficacious overtime than higher doses, 2) a traditional dose response effect of CPI-613 is not observed in AML patients thus far, and 3) a previous study in pancreatic cancer that showed remarkable synergy between CPI-613 at 500mg/m^2 in combination with standard chemotherapy.

## **2.0 Objectives**

### **2.1 Primary Objective**

To determine the feasibility of CPI-613 when administered with high dose cytarabine, and mitoxantrone in all three phases of salvage therapy (induction, and maintenance). The regimen will be considered feasible if  $\geq 50\%$  of patients eligible for maintenance therapy complete at least 3 cycles.

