## 5.0 Treatment Plan

Patients recruited at 500 mg/m^2 will receive this dose for all treatment phases.

Salvage Induction Cycle 1:

The dose of CPI-613 will be 500 mg/m^2/day or 1,500 mg/m^2/day given over 2 hours on days 1-5. Immediately following CPI-613 dosing 50 ml of D5W will be run through the central line. Cytarabine will be given following CPI-613 at 3gm/m^2 for age <60 or 1.5 gm/m^2 for age >60 in 500 mL NS over 3 hours every 12 hours for 5 doses starting on day 3. Mitoxantrone will be given at 6mg/m^2 daily for 3 doses given in 50 mL NS over 15 minutes after 1st, 3rd and 5th doses of cytarabine.

Dose modifications for cytarabine and mitoxantrone are as follows (Please see section 6 for CPI-613 dose modifications):

Hold Cytarabine and notify physician if:

- Bilirubin 1.5-3: Consider Decrease dose by 25%.
- Bilirubin greater than 3: Consider Decrease dose by 50%.
- Cr Cl less than 60 mL/min: Consider dose reduction.
- Hold mitoxantrone and notify physician if:
- Bilirubin greater than 3: Consider Decrease dose by 25%.

All dose modifications are at the discretion of the treating physician.

Salvage Induction Cycle 2 (Optional, at the discretion of the treating physician):

A repeat of the initial cycle as outlined above or at the discretion of the treating physician an abbreviated second cycle can be given. In the abbreviated course CPI-613 is given as above on days 1-3, cytarabine given as above for 3 doses starting on day 2, mitoxantrone given as above after the first and third cytarabine doses.

Salvage Consolidation:

All responding patients are eligible for consolidation therapy with up to 2 cycles of the abbreviated course of CPI-613 at 500 mg/m^2/day or 1,500 mg/m^2/day, high dose cytarabine and mitoxantrone. Responding patients can be removed from trial at any time to receive a stem cell transplant at the discretion of the treating physician. Patients can move to maintenance following 1, 2 or no cycles of consolidation at the discretion of the treating physician.

Maintenance Therapy:

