Any patient that has completed all planned consolidation therapy (i.e. 0, 1 or 2 cycles) and refuses or is not eligible for a stem cell transplant may receive maintenance therapy with CPI-613. The dose for the maintenance phase of treatment in this study is 2,500 mg/m^2 except for patients who received 500 mg/m^2 at induction. Patients receiving 500 mg/m^2 at induction will continue with this dose during maintenance therapy. Patients may continue on maintenance therapy until evidence of disease progression, availability of stem cell transplant or occurrence of intolerable side effects.

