### Analysis Plan:

The primary objective of determining the feasibility of administering CPI-613 in combination with high dose cytarabine and mitoxantrone during induction, consolidation and maintenance therapies will be completed by determining the percentage of patients eligible for maintenance therapy who complete at least 3 cycles. If  $\geq 50\%$  of eligible patients complete 3 cycles of maintenance therapy we will consider this regimen feasible for future study. Given an estimated response rate of 50% and a 25% attrition to stem cell transplant, if we enroll 60 patients we should be able to assess feasibility of maintenance in approximately 22 patients. With 22 evaluable patients, a two-sided 95.0% confidence interval using the large sample normal approximation will extend 22% in either direction from the observed value when the expected value is 50%. Within a dose we should be able to estimate feasibility in 7 patients with a 95% confidence interval extending 36% in either direction.

Participants will also be followed and analyzed for secondary outcomes of response rate and overall survival both overall and by dose. Participants will be monitored for survival through routine follow-up visits. Confidence intervals will be calculated around the estimates of the response rate (CR and CRi). Assuming a response rate of 0.5, with 60 participants, we would be able to create 95 percent confidence intervals with a 0.13 margin of error (0.37, 0.63). We will use Kaplan-Meier estimation to analyze overall survival. The frequency of toxicities experienced by the participants will be presented by type and grade in an effort to monitor and report safety of the treatment.

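### The 50% rule measures feasibility of maintenance among eligible patients, so it cannot support the all-phase feasibility verdict stated in Sections 2.1 and 10

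*Combined protocol and SAP*

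**What the plan says.** Section 2.1 gives the objective as feasibility "in all three phases of salvage therapy (induction, and maintenance"). It announces three phases and lists two; consolidation is missing. The Analysis Plan in Section 10 restates the aim as feasibility of CPI-613 "in combination with high dose cytarabine and mitoxantrone during induction, consolidation and maintenance therapies".

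Both places give a single criterion. Section 10 says the objective will be met by "determining the percentage of patients eligible for maintenance therapy who complete at least 3 cycles". If at least half do so, "we will consider this regimen feasible for future study".

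The treatment plan fixes who can enter that denominator. Under Section 5.0, "All responding patients are eligible for consolidation therapy with up to 2 cycles". A patient who has completed planned consolidation (which may be no cycles) and "refuses or is not eligible for a stem cell transplant may receive maintenance therapy with CPI-613". The Schema also admits patients facing a significant delay to transplant; Section 5.0 does not. The expected denominator comes from "Given an estimated response rate of 50% and a 25% attrition to stem cell transplant", giving approximately 22 patients from 60 enrolled and 7 within a dose.

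Response, overall survival and toxicity are secondary (Section 2.2). Sixty-day mortality and the comparison of complete response with a historical cohort are exploratory (Section 10). None carries a threshold that enters the feasibility decision, and neither section gives a completion criterion for induction or consolidation.

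**The concern.** The declared conclusion is wider than the quantity measured. A proportion conditional on being eligible for maintenance is informative about maintenance. It says nothing about how many patients got through induction to that point. Induction deaths and non-responses leave the denominator and do not count against the verdict, so the rule would give the same answer for a regimen that brought most patients to maintenance and for one that brought few.

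This matters because the feasibility verdict is the main product of the pilot: Section 5.3 gives the purpose as deciding whether the regimen can be taken into larger trials. A report could state that the three-phase regimen is feasible when only a small share of treated patients completed it.

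The rule also requires no minimum number of eligible patients, so the verdict could rest on very few.

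**Working it through.** **Inputs.** From Section 10: 60 enrolled, 50% response, 25% attrition to transplant, a pass mark of 50% of eligible patients, and a historical response rate of 41%. From Sections 5.3 and 10: 20 patients per dose.

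**1. The plan's own denominator.** Eligible = enrolled × response × (1 − transplant attrition).
- Overall: 60 × 0.50 × 0.75 = 22.5, against approximately 22 stated. It reproduces.
- Per dose: 20 × 0.50 × 0.75 = 7.5, against 7 stated. It reproduces.

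The calculation multiplies by the response rate, which confirms that the plan itself places non-responders outside the denominator.

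**2. Who is outside it.** 60 − 22 = 38 patients (63%). Non-responders: 60 × 0.50 = 30. Transplant: 30 × 0.25 = 7.5, about 8.

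**3. What a pass means over all enrolled.** Half of 22 is 11. 11/60 = 18.3%, exact (Clopper-Pearson) 95% CI 9.5% to 30.4%.

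At the historical response rate: 60 × 0.41 × 0.75 = 18.45, about 18 eligible. Half of 18 is 9, and 9/60 = 15%. Non-responders would then be 60 × 0.59 = 35.4, or 59%.

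**4. The 50% mark cannot simply be moved to all enrolled patients.** Even if all 22 eligible patients complete, 22/60 = 37%, so a 50% requirement would fail at the plan's own values.

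**5. Behaviour of the rule by number eligible.** P(declare feasible) = P(X ≥ k), where X is binomial(n, p), k is the smallest whole number at or above n/2, and p is the true completion rate among eligible patients. The values of p are assumptions chosen to show the range. The plan does not say that the 50% mark will be applied within a dose; n = 7 is used because it is the plan's per-dose number.

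| Eligible n | Needed k | p = 0.40 | p = 0.60 |
|---|---|---|---|
| 22 (planned) | 11 | 0.23 | 0.88 |
| 18 (41% response) | 9 | 0.26 | 0.86 |
| 13 (30% response, assumed) | 7 | 0.23 | 0.77 |
| 7 (planned per dose) | 4 | 0.29 | 0.71 |

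At p = 0.40 the chance of a pass rises only modestly and unevenly as n falls, because an exact tie passes when n is even and cannot occur when n is odd. At p = 0.60 the chance of a pass generally falls as n falls.

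**The case against.** The strongest defence is that a pilot may reasonably put its go-forward rule on maintenance. Section 1.5 says the same combination was already given in a phase I study. Earlier phases are not ignored either: response is reported with confidence intervals, survival by Kaplan-Meier and toxicity by type and grade, and 60-day mortality is compared with a historical cohort. The safety committee described in Appendix B reviews all grade 5 and unexpected grade 4 events and can suspend the trial. All of this stands, and it makes a maintenance-only rule a defensible choice. It does not close the gap, because none of these measures enters the feasibility decision, whose stated verdict covers all phases.

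Four stronger readings are tempting, and the documents do not support them.
- A reader might infer that the plan expects most patients to fail before maintenance. At planning values half are non-responders, and about 8 of the 38 outside the denominator go to transplant, which is not failure.
- A reader might infer that poor induction results make a chance pass more likely in general. That holds, unevenly, only when true completion is below 50%. Striking figures can be produced at p = 0.40 (0.37 at n = 10, 0.52 at n = 4), but both use an even n where ties pass; n = 9 gives 0.27 and n = 5 gives 0.32. They also imply response rates of about 22% (10/45) and 9% (4/45), where 45 = 60 × 0.75, far from the 41% to 50% in the documents.
- A reader might infer that any toxicity before maintenance removes a patient from the denominator. Eligibility follows planned consolidation of 0, 1 or 2 cycles, so a responder who stops consolidation early might still be eligible and count as a non-completer. The criterion is eligibility, not starting maintenance.
- The missing word in Section 2.1 might be read as a narrower objective. Sections 2.2, 5.3 and 10 name all three phases, so it is a drafting slip.

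**Conclusion.** The point holds as a mismatch between scope and rule. The maintenance proportion is a valid estimate of what it measures. An all-phase feasibility verdict does not follow from it, because death and non-response in induction cannot count against it.

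Under the plan's assumptions the regimen would be called feasible with 18% of enrolled patients completing 3 maintenance cycles, or with 15% at the historical response rate. Both percentages assume 60 enrolled and 25% transplant attrition among responders, and both include transplanted responders among those not completing. They show how little the rule says about the whole sequence and are not failure rates.

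The absence of a minimum denominator is a secondary weakness. Within the range the documents make plausible, it moves the chance of a wrong pass at 40% true completion only from 0.23 to 0.29. The change should be made before analysis, but it does not call the trial's design into question.

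**What to change.** - Keep the 50% rule, and reword its verdict in Sections 2.1 and 10 as feasibility of maintenance among eligible patients.
- Add to the primary analysis one table over all patients who start induction, with exact 95% intervals: the proportions who respond, leave for transplant (as its own category), become eligible for maintenance, start maintenance, and complete at least 3 cycles.
- Draw no all-phase verdict from the 50% rule; describe all-phase feasibility from that table only.
- Use one definition of eligibility for maintenance. The Schema and Section 5.0 differ on patients facing a transplant delay and must be reconciled. State also how a responder who stops consolidation early is counted.
- Restore consolidation to the list of phases in Section 2.1.

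The cost is wording and one table. The data collection forms in Appendices D to G show no field for start of maintenance or for transplant, so these two items need recording if they are not captured elsewhere. The all-treated figures will look less favourable than the conditional one. Treatment and sample size do not change.

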### **2.2 Secondary Objectives**

To observe the response rate (CR, and CRi) of CPI-613 in combination with high dose cytarabine and mitoxantrone.

To observe the overall survival of patients treated with CPI-613 in combination with high dose cytarabine and mitoxantrone in induction, consolidation and maintenance.

To monitor toxicities experienced by patients treated with CPI-613 in combination with high dose cytarabine and mitoxantrone in induction, consolidation and maintenance.

## **3.0 Patient Selection**

This clinical trial can fulfill its objective only if patients appropriate for this trial are enrolled. All relevant medical and other considerations should be taken into account when deciding whether this protocol is appropriate for a particular patient. Physicians should consider the risks and benefits of any therapy, and therefore only enroll patients for whom this treatment is appropriate.

### 3.1 Inclusion Criteria

- 3.1.1 Patients must have histologically or cytologically documented relapsed and/or refractory Acute Myeloid Leukemia or granulocytic sarcoma.
- 3.1.2 ECOG Performance Status of  $\leq 3$ .
- 3.1.3 Must be  $\geq 18$  years of age.
- 3.1.4 Expected survival  $> 3$  months.
- 3.1.5 Women of child-bearing potential (i.e., women who are pre-menopausal or not surgically sterile) must use accepted contraceptive methods (abstinence, intrauterine device [IUD], oral contraceptive or double barrier device), and must have a negative serum or urine pregnancy test within 1 week prior to treatment initiation. (Note: Pregnant patients are excluded because the effects of CPI-613 on a fetus are unknown.)
- 3.1.6 Fertile men must practice effective contraceptive methods during the study period, unless documentation of infertility exists.
- 3.1.7 Mentally competent, ability to understand and willingness to sign the informed consent form.
- 3.1.8 No radiotherapy, treatment with cytotoxic agents (except CPI-613), treatment with biologic agents or any anti-cancer therapy within the 2 weeks prior to treatment with CPI-613. Hydroxyurea and oral tyrosine kinase inhibitors being used without Grade  $\leq 2$  toxicity can be taken until day 1 of therapy. Patients must have fully recovered from the acute, non-hematological, non-infectious toxicities of any prior treatment with cytotoxic drugs, radiotherapy or other anti-cancer modalities (returned to baseline status as noted before most recent treatment). Patients with persisting, non-hematologic, non-infectious toxicities from prior treatment  $\leq$  Grade 2 are eligible, but must be documented as such.
- 3.1.9 Laboratory values  $\leq 2$  weeks must be:
  - Adequate hepatic function (aspartate aminotransferase [AST/SGOT]  $\leq 3$  times upper normal limit [UNL], alanine aminotransferase [ALT/SGPT]  $\leq 3$  times UNL ( $\leq 5$  times ULN if liver metastases present), bilirubin  $\leq 1.5$  times UNL).
  - Adequate renal function (serum creatinine  $\leq 1.5$  mg/dL or 133  $\mu$ mol/L).
- 3.1.10 Left Ventricular Ejection Fraction (by TTE, MUGA or cardiac MRI) sufficient to safely administer mitoxantrone as determined by the treating physician

### 3.2 Exclusion Criteria

- 3.2.1 Serious medical illness, such as significant cardiac disease (e.g. symptomatic congestive heart failure, unstable angina pectoris, myocardial infarction within the past 6 months, uncontrolled cardiac arrhythmia, pericardial disease or New York Heart Association Class III or IV), or

severe debilitating pulmonary disease, that would potentially increase patients' risk for toxicity.

- 3.2.2 Patients with active central nervous system (CNS) or epidural tumor.
- 3.2.3 Albumin <2.0 g/dL or <20 g/L.
- 3.2.4 Any active uncontrolled bleeding, and any patients with a bleeding diathesis (e.g., active peptic ulcer disease).
- 3.2.5 Pregnant women, or women of child-bearing potential not using reliable means of contraception (because the teratogenic potential of CPI-613 is unknown).
- 3.2.6 Lactating females because the potential of excretion of CPI-613 into breast milk. (**Note:** Lactating females are excluded because the effects of CPI-613 on a nursing child are unknown.)
- 3.2.7 Fertile men unwilling to practice contraceptive methods during the study period.
- 3.2.8 Life expectancy less than 3 months.
- 3.2.9 Any condition or abnormality which may, in the opinion of the investigator, compromise the safety of patients.
- 3.2.10 Unwilling or unable to follow protocol requirements.
- 3.2.11 Patients with large and recurrent pleural or peritoneal effusions requiring frequent drainage (e.g. weekly). Patients with any amount of clinically significant pericardial effusion.
- 3.2.12 Active heart disease including symptomatic coronary artery disease, uncontrolled arrhythmias, or symptomatic congestive heart failure.
- 3.2.13 Evidence of ongoing, uncontrolled infection.
- 3.2.14 Patients with known HIV infection. (**Note:** Patients with known HIV infection are excluded because patients with an immune deficiency are at increased risk of lethal infections when treated with marrow-suppressive therapy, and because there may be unknown or dangerous drug interactions between CPI-613 and anti-retroviral agents used to treat HIV infections.)
- 3.2.15 Patients receiving any other standard or investigational treatment for their cancer, or any other investigational agent for any indication within the past 2 weeks prior to initiation of CPI-613 treatment (the use of Hydrea is allowed).
- 3.2.16 Patients who have received immunotherapy of any type within the past 4 weeks prior to initiation of CPI-613 treatment.
- 3.2.17 Requirement for immediate palliative treatment of any kind including surgery.
- 3.2.18 Patients that have received a chemotherapy regimen with stem cell support in the previous 6 months.

### **3.3 Inclusion of Women and Minorities**

Both men and women and members of all races and ethnic groups are eligible for this trial.

CCCWFU 22215

Comprehensive Cancer Center of Wake Forest University

An Open Label Study to Evaluate the Feasibility of CPI-613 Given with High Dose Cytarabine and  
Mitoxantrone in Patients with Relapsed or Refractory Acute Myeloid Leukemia (AML)

**NCT Clinicaltrials.gov:** NCT02484391

## 4.0 Registration Procedures

All patients entered on any CCCWFU trial, whether treatment, companion, or cancer control trial, **must** be linked to the study in EPIC within 24 hours of Informed Consent. Patients **must** be registered prior to the initiation of treatment.

You must perform the following steps in order to ensure prompt registration of your patient:

1. Complete the Eligibility Checklist (Appendix A)
2. Complete the Protocol Registration Form (Appendix B)
3. Alert the Cancer Center registrar by phone, *and then* send the signed Informed Consent Form, Eligibility Checklist and Protocol Registration Form to the registrar, either by fax or e-mail.

Contact Information:

Protocol Registrar [contact]

Protocol Registrar [contact]

Protocol Registrar E-MAIL ([[contact]](mailto:[contact]))

\*Protocol Registration is open from 8:30 AM - 4:00 PM, Monday-Friday.

4. Fax/e-mail ALL eligibility source documents with registration. Patients **will not** be registered without all required supporting documents.

Note: If labs were performed at an outside institution, provide a printout of the results. Ensure that the most recent lab values are sent.

To complete the registration process, the Registrar will:

- assign a patient study number
- assign the patient a dose
- register the patient on the study

## 5.0 Treatment Plan

Patients recruited at 500 mg/m^2 will receive this dose for all treatment phases.

Salvage Induction Cycle 1:

The dose of CPI-613 will be 500 mg/m^2/day or 1,500 mg/m^2/day given over 2 hours on days 1-5. Immediately following CPI-613 dosing 50 ml of D5W will be run through the central line. Cytarabine will be given following CPI-613 at 3gm/m^2 for age <60 or 1.5 gm/m^2 for age >60 in 500 mL NS over 3 hours every 12 hours for 5 doses starting on day 3. Mitoxantrone will be given at 6mg/m^2 daily for 3 doses given in 50 mL NS over 15 minutes after 1st, 3rd and 5th doses of cytarabine.

Dose modifications for cytarabine and mitoxantrone are as follows (Please see section 6 for CPI-613 dose modifications):

Hold Cytarabine and notify physician if:

- Bilirubin 1.5-3: Consider Decrease dose by 25%.
- Bilirubin greater than 3: Consider Decrease dose by 50%.
- Cr Cl less than 60 mL/min: Consider dose reduction.
- Hold mitoxantrone and notify physician if:
- Bilirubin greater than 3: Consider Decrease dose by 25%.

All dose modifications are at the discretion of the treating physician.

Salvage Induction Cycle 2 (Optional, at the discretion of the treating physician):

A repeat of the initial cycle as outlined above or at the discretion of the treating physician an abbreviated second cycle can be given. In the abbreviated course CPI-613 is given as above on days 1-3, cytarabine given as above for 3 doses starting on day 2, mitoxantrone given as above after the first and third cytarabine doses.

Salvage Consolidation:

All responding patients are eligible for consolidation therapy with up to 2 cycles of the abbreviated course of CPI-613 at 500 mg/m^2/day or 1,500 mg/m^2/day, high dose cytarabine and mitoxantrone. Responding patients can be removed from trial at any time to receive a stem cell transplant at the discretion of the treating physician. Patients can move to maintenance following 1, 2 or no cycles of consolidation at the discretion of the treating physician.

Maintenance Therapy:

Any patient that has completed all planned consolidation therapy (i.e. 0, 1 or 2 cycles) and refuses or is not eligible for a stem cell transplant may receive maintenance therapy with CPI-613. The dose for the maintenance phase of treatment in this study is 2,500 mg/m^2 except for patients who received 500 mg/m^2 at induction. Patients receiving 500 mg/m^2 at induction will continue with this dose during maintenance therapy. Patients may continue on maintenance therapy until evidence of disease progression, availability of stem cell transplant or occurrence of intolerable side effects.

